## Treatment Site Application Instructions

### Abdominal Test Site

1. Using repeated back-and-forth strokes of the sponge for thirty (30) seconds, completely wet the treatment area with test material.
2. Allow the area to air-dry for three (3) minutes. Do not blot or wipe away.

### Inguinal Test Site

1. Using repeated back-and-forth strokes of the sponge for two (2) minutes, completely wet the treatment area with test material.
2. Allow the area to air-dry for three (3) minutes. Do not blot or wipe away.

### ZuraPrep Vehicle (negative control)

## Treatment Site Application Instructions

### Abdominal Test Site

1. Using repeated back-and-forth strokes of the sponge for thirty (30 ) seconds, completely wet the treatment area with test material.
2. Allow the area to air-dry for three (3) minutes. Do not blot or wipe away.

### Inguinal Test Site

1. Using repeated back-and-forth strokes of the sponge for two (2) minutes. Completely wet the treatment area with test material.
2. Allow the area to air-dry for three (3) minutes. Do not blot or wipe away.

## 14.8 Confirmation of Release and Receipt of Study Materials

## **CONFIRMATION OF RELEASE and RECEIPT OF STUDY MATERIALS**

**Investigator:** M. [name], CCRP  
**Study No:** MBT 865-105  
**Test Site:** MicroBioTest

Quantity (Units)	Description	ID/Lot Number	Exp. Date

Supplies Released to Site by: \_\_\_\_\_  
Sponsor Signature \_\_\_\_\_

Supplies Sent to Site (Date): \_\_\_\_\_

Supplies Checked and Verified by: \_\_\_\_\_

---

Print Name, Title

Once the supplies have been verified and this form is signed / dated, a signature copy will be sent to the sponsor representative: [REDACTED]

## 14.9 Study Material Disposition Form

Use one form for each study material.

Study Number: MBT 865-105	Investigator: M. [name], CCRP	Investigator Site: MicroBioTest
----------------------------------	--	--

Study Material ID:	Date Received:	Quantity Received:	Lot Number/ Serial Number:	Date Returned to Sponsor:

## 14.10 Procedure for Neutralization Validation

### 1. Background

The sampling solution, SS, sterile [75mM phosphate buffer ( [REDACTED] ) containing [REDACTED] lecithin, [REDACTED] Tween® 80, and [REDACTED] Tamol, [REDACTED] ] is a buffered detergent solution that is commonly used in studies where microbial sampling of skin is conducted. Neutralizers have been added to inactivate the antimicrobial, isopropyl alcohol and chlorhexidine gluconate, present in test treatments. The effectiveness and toxicity of this neutralizer system must be assessed to demonstrate that there is no effect on the growth of microorganisms and that the active ingredient is inactivated.

The density of normal human skin flora generally ranges from  $10^2$  to  $10^5$  CFU/cm^2 depending on the body site. However, since significant neutralizer or toxic effects are more easily detected at a lower cell density, the efficacy and toxicity of this neutralizer system will be assessed against a lower bacterial concentration.

This is a test where the study materials are applied to the abdomen and the treated areas will be sampled. After sampling, [REDACTED], a selected representative of normal skin flora will be added into a portion of each sample. Each sample will then be processed using procedures in accordance with ASTM E1054-08.

### 2. Objective

This control assay will determine the ability of the SS to completely neutralize the active ingredients in the test treatments when applied to the abdomen by recovering and quantifying microorganism populations on agar media and is appropriate for antimicrobial agents that can be chemically inactivated or diluted to sub-inhibitory levels.

### 3. Subject Entry Criteria

[REDACTED] subjects will be used for the neutralization validation required for this study. Each subject must meet the inclusion and exclusion criteria described in Sections 4.1 and 4.2 except for the baseline bacterial count, the 72-hour exclusion from showering/bathing and the length of the washout period. No minimum bacterial count is required and the washout period is only necessary for 7 days (not 14 days). The subjects will be asked to provide information on demographics and inclusion/exclusion criteria and sign the Consent and Authorization Forms before beginning the 7-day washout period. When the subjects return to begin their participation in the study they will again be asked to provide information relative to inclusion/exclusion criteria. If they

meet all inclusion/exclusion criteria, they may be enrolled. The subjects will be identified by the letter "N" for neutralization and a subject number of [REDACTED].

The test, vehicle and reference control articles will be applied to the abdomen regions using bilateral applications so that [REDACTED] applications are performed for each treatment using bilateral application (a total of [REDACTED] subjects). One area will be located on one side of the body and the remaining area on the other side.

The treatments per subject will be randomized. The randomization scheme will be generated before the test.

#### 4. Test Organisms

The test organisms for this study are:

- a. [REDACTED]
- b. [REDACTED]

#### 5. Treatment Materials

- a. ZuraPrep™ [REDACTED] (containing 70% v/v Isopropyl Alcohol)
- b. ChloraPrep® [REDACTED] (Scrub Teal® Tint) (containing 2% chlorhexidine gluconate)
- c. ZuraPrep Vehicle (negative control)

#### 6. Materials, Supplies and Equipment

See section 3.4.3 of the MBT 865-105 Protocol. In addition, 70% isopropyl alcohol swabs.

#### 7. In-vivo Test Procedures (collection of samples)

**Preparation of Test Area and Post-Prep Sampling:** Neutralization samples will be taken from the abdomen. The subject number, location of the prep application, location of the sites sampled within the prep area, and the time of sample collection will be documented on the CRF. The subject will be treated with the study materials based on the following.

- For each side of the body, mark the abdominal test areas using a sterile 2" x 5" template. The 2" x 5" areas will be delineated with each containing one 1" x 1" sampling site.
- After the test areas are marked, each area will be processed using three 70% isopropyl alcohol swabs for a total of one minute to prepare the site; the areas

will be allowed to dry. This step is to prepare the skin for the neutralization test.

- Prep the test areas with the appropriate treatment according to the instructions provided in Appendix 14.7, MBT 865-105 Protocol for groin.
- Using the scrub cup technique at approximately 30 seconds post-prep, begin collecting samples from each site using SS. This technique is described in Section 5.2.1 of the MBT 865-105 Protocol.

8. In-vitro Test Procedures (performed using the collected samples in accordance with ASTM E1054-08)

8.1. Inoculum Preparation: For each test organism, the organism will be prepared from and overnight broth culture ( $24 \pm 4$  hours) grown in TSB at  $35 \pm 2$ C to yield a concentration of approximately [REDACTED] CFU/mL. The culture will be diluted using PBW in a manner such that [REDACTED] CFU/mL will be delivered into the neutralizer tube (a [REDACTED] aliquot of the collected SS sample will be used).

8.2 Test: (note – the reference to test article applies to test article, the vehicle and the reference control article; all procedures outlined, where applicable will employ all articles.)

8.2.1 Neutralizer effectiveness (Test 1):

- a. Out of the [REDACTED] aliquot of sampling solution taken from the volunteer, [REDACTED] [REDACTED] will be transferred to a new sterile tube and inoculated with the challenge microorganism so that the final concentration will equal [REDACTED] colony-forming units (CFU) / mL of the challenge microorganism (the prepared inoculum will be diluted using PBW to achieve the desired concentration, a [REDACTED] aliquot from the [REDACTED] dilution will be used).
- b. Within one min after the addition of the challenge microorganism, the microorganisms will be enumerated by standard microbiological methods extant in the laboratory.
- c. Duplicate [REDACTED] aliquots will be removed and plated using TSA+N pour plates.
- d. After 30 minutes, the microorganisms will be enumerated a second time using the same procedures.
- e. Duplicate [REDACTED] aliquots will be removed and plated using TSA+N pour plates.

8.2.2 Neutralizer toxicity (Test 2):

- a. A [REDACTED] aliquot of sampling solution will be inoculated with the challenge microorganism so that the final concentration will equal [REDACTED] colony-forming units (CFU) / mL of the challenge microorganism in the same manner

as Test 1.

- b. Within one min after the addition of the challenge microorganism, the microorganisms will be enumerated by standard microbiological methods extant in the laboratory.
- c. Duplicate [REDACTED] aliquots will be removed and plated using TSA+N pour plates.
- d. After 30 minutes, the microorganisms will be enumerated a second time using the same procedures.
- e. Duplicate [REDACTED] aliquots will be removed and plated using TSA+N pour plates.
- f. This procedure will be repeated two times for a total of three replicates.

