#### 8.2.4 Test article control (Test 4):

- a. A [REDACTED] aliquot of the test or control article will be inoculated with a volume of the challenge microorganism so that the resulting suspension contains [REDACTED] CFU/mL in the same manner as Test 1.
- b. Within one min the microorganisms will be enumerated (in triplicate) by standard microbiological methods extant in the laboratory.
- c. Duplicate [REDACTED] aliquots will be removed and plated using TSA pour plates.
- d. After 30 minutes, the microorganisms will be enumerated a second time using the same procedures.
- e. Duplicate [REDACTED] aliquots will be removed and plated using TSA pour plates.
- f. This procedure will be repeated two times for a total of three replicates.

8.3. Incubation:

All plates for Tests 1, 2, 3 and 4 will be incubated for  $48\pm2$  hours at  $35^\circ\pm2^\circ\text{C}$ .

8.4. Interpretation of data:

- a. The number of surviving challenge microorganisms for each replicate from each test will be average count of the three plates.
- b. The number of survivor values will be transformed to  $\log_{10}$ .
- c. The number of survivors ( $\log_{10}$ ) from each test (1, 2, and 4) will be compared to the test microorganism viability population (test 3).
- d. Neutralization aspects of the sampling solution will be considered adequate if the mean  $\log_{10}$  CFU/mL of Test 1 is not more than 0.20  $\log_{10}$  less than the mean  $\log_{10}$  CFU/mL of Test 3 (Mean  $\log_{10}$  CFU/mL from Test 3 – Mean  $\log_{10}$  CFU/mL from Test 1 using corresponding time points).
- e. The sampling solution will be considered non-toxic if the mean  $\log_{10}$  CFU/mL of Test 2 is not more than 0.20  $\log_{10}$  less than the mean  $\log_{10}$  CFU/mL of Test 3 (Mean  $\log_{10}$  CFU/mL from Test 3 – Mean  $\log_{10}$  CFU/mL from Test 2 using corresponding time points).
- f. The mean  $\log_{10}$  CFU/mL from Test 4 must be at least 0.20  $\log_{10}$  less than the mean  $\log_{10}$  CFU/mL of Test 3.
- g. The amount of CFU added for each aspect must be confirmed to yield a final suspension containing [REDACTED]/mL (validated in test 3).
- h. The sterility controls must be negative for growth.

8.5. Controls:

8.5.1 Sterility control:

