Triplicate plates of TSA and TSA+N used will be incubated with the test. In addition, triplicate [REDACTED] aliquots of sampling solution and PBW will be plated using TSA pour plates used for a particular test date. All plates will be incubated with the test.

8.5.2 Challenge microorganism confirmation:

In order to confirm growth consistent with the challenge microorganism, Gram stains will be performed from a representative colony from a test plate. The colony morphology will be noted as well.

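### The neutralizer-effectiveness test has no uninoculated skin-sample blank, so any residual flora can only help it pass (a minor gap, conditional on flora surviving)

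*Combined protocol and SAP*

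**What the plan says.** Section 5.2.5 requires the neutralizer system to be validated before study start, and Appendix 14.10 gives the procedure.

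- **Sample (Appendix 14.10, sections 1, 7 and 8.2.1).** The abdomen is swabbed with 70% isopropyl alcohol for one minute in total, treated by the groin instructions, and scrub-cup sampled at about 30 seconds. Then "a selected representative of normal skin flora will be added into a portion of each sample". In 8.2.1, part of the collected fluid "will be transferred to a new sterile tube and inoculated with the challenge microorganism so that the final concentration will equal" a redacted level.
- **Plating (8.2.1).** Within one minute of inoculation and again after 30 minutes, "Duplicate [REDACTED] aliquots will be removed and plated using TSA+N pour plates".
- **What is counted (8.4(a)).** "The number of surviving challenge microorganisms for each replicate from each test will be average count of the three plates". (8.2.1 specifies duplicate plates, not three; that mismatch does not affect this point.)
- **Comparator (8.2.3).** Test 3 is inoculated phosphate-buffered water, which contains no skin flora.
- **Acceptance (8.4(d)).** "Neutralization aspects of the sampling solution will be considered adequate if the mean" log10 count for Test 1 falls no more than 0.20 log10 short of Test 3 at the same time point. An excess in Test 1 cannot fail.
- **Controls (8.5).** Sterility plates cover the media, the sampling solution and the buffer. For identity, "Gram stains will be performed from a representative colony from a test plate", and colony morphology is noted.

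Amendment 1 adds a second sampling site in each test area but does not describe it as a blank.

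**The concern.** Test 1 is the only arm of the validation whose fluid has touched skin. Flora left on the site enter its count and not that of Test 3, and 8.4(a) credits them to the challenge organism. Because 8.4(d) penalizes only a shortfall, the error runs one way: residual flora can offset a real loss of challenge organism but cannot cause a failure.

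The validation exists to rule out continued killing in the tube. Section 5.2.3 allows trial samples up to 30 minutes before plating. If an active product went on killing during that time, log10 reductions and responder rates for the active products would be overstated, including the primary 10-minute rate. A validation that is too easy to pass gives less assurance against this than its 0.20 log10 limit suggests.

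**Working it through.** The plan gives no figure to reproduce here. The check is arithmetic on the 0.20 log10 criterion.

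**Inputs**
- Margin: 0.20 log10, from Appendix 14.10, 8.4(d).
- Spike N (CFU/mL): redacted. Section 1 of the appendix says only that a lower cell density is used. Assumed 30, 100 and 1000.
- Residual flora f (CFU/mL in the sample): not measured. Assumed 5 and 10.
- Normal skin density: 10^2 to 10^5 CFU/cm2, from section 1 of the appendix.
- Cup area over fluid volume: redacted. Assumed 0.3 to 1.29 cm2/mL.

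**Intended tolerance.** 10^(-0.20) = 0.631, so with no flora the largest loss that passes is 1 - 0.631 = 36.9%.

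**With flora present.** Let s be the true survival of the challenge organism. Two assumptions about the flora bracket the plausible range:
- Flora die at the same rate as the challenge: (N + f)s ≥ 0.631N, so the largest passing loss is 1 - 0.631/(1 + f/N).
- Flora are unaffected: Ns + f ≥ 0.631N, so it is 1 - 0.631 + f/N.

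| f | N | f/N | Same rate | Unaffected |
|---|---|---|---|---|
| 5 | 30 | 0.167 | 1 - 0.631/1.167 = 45.9% | 0.369 + 0.167 = 53.6% |
| 5 | 100 | 0.050 | 39.9% | 41.9% |
| 5 | 1000 | 0.005 | 37.2% | 37.4% |
| 10 | 30 | 0.333 | 52.7% | 70.2% |
| 10 | 100 | 0.100 | 42.6% | 46.9% |
| 10 | 1000 | 0.010 | 37.5% | 37.9% |

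If flora died faster than the challenge, the bias would be smaller than the first column shows.

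**Flora needed to hide a 50% loss.** Unaffected flora: 0.631 - 0.50 = 13.1% of the spike. Same rate: 0.631/0.50 - 1 = 26.2%. That is 3.9 to 7.9 CFU/mL at N = 30, 13.1 to 26.2 at N = 100, and 131 to 262 at N = 1000.

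**Are such levels plausible?** f = skin density × 10^(-total log10 reduction) × (area/volume), where the reduction is from swab plus product:
- 10^3 CFU/cm2 less 2 log10: 10 × 0.3 to 10 × 1.29 = 3.0 to 12.9 CFU/mL.
- 10^3 less 3 log10: 0.3 to 1.3 CFU/mL.
- 10^5 less 3 log10: 30 to 129 CFU/mL.
- 10^5 less 4 log10: 3.0 to 12.9 CFU/mL.

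At 1.3 CFU/mL, even a spike of 30 gives only 39.5% to 41.2% against the intended 36.9%; larger spikes give less. The bias therefore needs a low spike together with high starting flora or weak disinfection.

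**The case against.** The strongest reply is that the protocol already deals with residual flora. The swabbing is there to prepare the skin for this test, and it is followed by the groin application, with two minutes of scrubbing, on the abdomen, which has the lower baseline range in Table 3.2. For an active product, flora must survive both steps. The vehicle probably leaves the most flora, but it has no active ingredient to neutralize. Spike, volumes and cup area are redacted, and neither ASTM E1054-08 nor the laboratory's standard methods, either of which might call for a sample blank, can be seen here.

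Most of this stands as a limit on size. It does not close the gap: the appendix neither measures what remains nor sets a limit on it. A Gram stain and morphology from one representative colony cannot quantify a mixed plate, especially when the challenge organism is itself chosen to represent skin flora.

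Two stronger readings do not hold. A reader might infer that a complete kill could pass. With f = 20 and N = 30, the unaffected-flora formula does give 0.369 + 0.667 > 1. But that needs a fluid that kills every challenge cell and spares all the flora; at a shared rate the limit is 1 - 0.631/1.667 = 62%, and nothing in the documents supports 20 CFU/mL. A reader might also take the relaxed entry criteria (Appendix 14.10, section 3) as a sign of high flora. Waiving the minimum count and the 72-hour bathing restriction, and shortening the washout to 7 days, should lower flora if anything.

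**Conclusion.** The gap is confirmed and minor. Test 1 has no background correction, and its one-sided comparison turns any residual flora into help toward passing. Its size is conditional on redacted and unmeasured quantities. For 5 CFU/mL of flora, the largest passing loss is 46-54%, 40-42% and about 37% at spikes of 30, 100 and 1000 CFU/mL. For 10 CFU/mL it is 53-70%, 43-47% and about 38%. The intended limit is 37%. The bias is negligible if swab plus product remove about 3 log10 or more from 10^3 CFU/cm2 or less.

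A reader might infer that neutralization failed or that the trial's reductions are inflated. The documents do not support that: they do not show that flora survived in harmful amounts. What they show is a control that the procedure omits.

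**What to change.** In Appendix 14.10, 8.2.1, add a step that plates duplicate uninoculated aliquots of each collected sample on TSA+N at the same two times as Test 1. Subtract their mean count from the Test 1 count before log transformation, and apply 8.4(d) to the corrected count. State beforehand how a corrected count of zero or below is handled. Reading the blank at both times removes the bias whether or not the flora die along with the challenge organism.

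The cost is 2 plates × 2 times = 4 extra plates per sample and slightly more counting error after subtraction. It needs no extra subjects or visits. The fluid should come from the part of the sample that is not inoculated; the volumes are redacted, so the laboratory must confirm that enough remains.

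Amendment 6 (July 2017) was issued after testing was complete. For samples already processed, the final report should give any uninoculated or morphology-specific Test 1 counts that exist. If there are none, it should say that residual flora were not measured.

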#### 8.2.3 Test microorganism viability control (Test 3):

- a. A [REDACTED] aliquot of PBW will be inoculated with a volume of the challenge microorganism so that the resulting suspension contains [REDACTED] CFU/mL in the same manner as Test 1.
- b. Within one min the microorganisms will be enumerated (in triplicate) by standard microbiological methods extant in the laboratory.
- c. Duplicate [REDACTED] aliquots will be removed and plated using TSA pour plates.
- d. After 30 minutes, the microorganisms will be enumerated a second time using the same procedures.
- e. Duplicate [REDACTED] aliquots will be removed and plated using TSA pour plates.
- f. This procedure will be repeated two times for a total of three replicates.

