### 3.4.3 Study Supplies Provided by Study Site

- Reference Control Article
- Treatment Material Disposition forms
- Product kits (toiletry items to be used by subjects during study)
- Consent / Authorization forms, IRB-approved
- Case report forms
- Sampling solution, sterile [REDACTED]
- Butterfield's sterile phosphate buffered water containing neutralizers, [REDACTED] ( [REDACTED] )
- High-purity deionized water, sterile
- Trypticase Soy Agar (TSA)
- Trypticase soy agar containing 0.5% Tween 80 and 0.07% lecithin (TSA+N)
- Transfer pipettes, polyethylene, sterile
- Serological pipettes ( [REDACTED] ), sterile, [REDACTED]
- Pipetting device, calibrated to accurately dispense [REDACTED]
- Tubes with sealable caps, polypropylene or glass, sterile
- Petri dishes, 100 mm, sterile
- Gloves, sterile
- Gauze, sterile (2" x 2")
- Marking templates, 5" x 5" & 1.5" x 5", sterile (for marking test sites)
- Non-toxic marking pen (Sharpie or equivalent)
- Rubber policemen, sterile
- Scrub cups ( [REDACTED] [REDACTED] ), sterile

- Timers or stopwatches
- Pipette Aid or similar apparatus
- Vortex mixer
- Surgical Clipper & clipper blades
- Water bath ( $45 \pm 2C$ )
- Incubator ( $30 \pm 2C$ )
- Disposable underwear for subjects
- Tryptic Soy Broth (for the Neutralization Validation Procedure only – See Appendix 14.10) (TSB)
- [REDACTED] Urine Strip Test (for Pregnancy) or equivalent.

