### 5.2.3 Bacterial Enumeration Methods

Following sample collection, 10-fold serial dilutions (1 mL sample + 9 mL PBW) will be prepared using Butterfield's phosphate buffered water with neutralizers (PBW). One mL aliquots of appropriate dilutions will be pour-plated in duplicate using trypticase soy agar containing neutralizers (TSA+N). Samples must be plated within 30 minutes of collection. After  $72 \pm 4$  hours of aerobic incubation at  $30 \pm 2$ C, colonies will be counted and viable cells in the original sample will be calculated according to Standard Operating Procedures. After incubation, plates may be refrigerated up to 48 hours prior to counting.

Raw colony counts from each dilution will be recorded on the appropriate CRFs for each subject. The average number of microorganisms recovered (CFU/cm^2) of skin for the screening and treatment day baseline samples will be calculated using the following formula to convert the plate CFU values into CFU/cm^2 of skin:

$$R = \log_{10} \left[ \frac{F \left( \frac{\sum c_i}{n} \right) D}{A} \right]$$

Where:

R = the average CFU count in  $\log_{10}$  scale per  $\text{cm}^2$  of skin.

F = total mL of stripping fluid added to the sampling cylinder ([REDACTED]);

$\sum c_i/n$  = average of the duplicate colony counts for each sample collected

D = Dilution of the plates counted ( $10^0$ ,  $10^1$ ,  $10^2$ ,  $10^3$ ,  $10^4$ , or  $10^5$ )

A = Inside area of the sampling cylinder ([REDACTED] [REDACTED])

Dilution may be reported as dilution factor, which is the base 10 logarithm of the dilution. In that case, the factor of 'D' in the equation above will be replaced with  $10^D$ .

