#### 5.2.5 Neutralizer Validation

The effectiveness of the neutralizer system must be validated prior to the study start date to demonstrate that the antimicrobial is effectively neutralized and there is no effect on the growth of microorganisms. A procedure that will include in-vivo sampling will be combined with an in-vitro evaluation using procedures in accordance with ASTM E1054-08. The procedure is attached as Appendix 14.10. These data must be provided in the final report.

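### The viability control (Test 3) in the neutralizer validation is suspended in a fluid defined as containing neutralizers, so the toxicity rule cannot see a loss that this fluid shares with the sampling solution

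*Combined protocol and SAP*

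**What the plan says.** Section 5.2.5 requires the neutralizer system to be validated before the study starts, including a demonstration that "there is no effect on the growth of microorganisms". The procedure is in Appendix 14.10.

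- **Control fluid.** In Test 3 (item 8.2.3) an "aliquot of PBW will be inoculated with a volume of the challenge microorganism so that the resulting suspension contains" a target count, which is redacted. Its "aliquots will be removed and plated using TSA pour plates", that is, on agar without neutralizers.
- **What PBW is.** The abbreviation is spelled out once, in Section 5.2.3, where serial dilutions of study samples "will be prepared using Butterfield's phosphate buffered water with neutralizers (PBW"). The supply list in Section 3.4.3 has one matching entry, "Butterfield's sterile phosphate buffered water containing neutralizers". The redaction there hides the composition, not the presence of neutralizers.
- **Materials for the validation.** Appendix 14.10, item 6 reads "See section 3.4.3 of the MBT 865-105 Protocol. In addition, 70% isopropyl alcohol swabs". No plain buffer is added.
- **Inoculum.** Items 8.1 and 8.2.1 dilute the challenge culture in PBW, and the other tests inoculate in the same manner.
- **Acceptance rule.** Under item 8.4(e), "The sampling solution will be considered non-toxic if the mean" log10 count of Test 2 falls no more than 0.20 below that of Test 3. Test 3 is also the reference for Tests 1 and 4.

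None of Amendments 1 to 8 changes the Test 3 fluid or the meaning of PBW.

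**The concern.** A toxicity test needs a reference in which the suspected agent is absent. The plan gives Test 3 neutralizer-free agar but, on its own definition, not a neutralizer-free suspension. Organisms in Tests 2 and 3 then sit in neutralizer-containing fluids for the same one and 30 minutes before plating. A loss caused in both fluids lowers both counts and disappears from their difference.

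At stake is whether the validation delivers what Section 5.2.5 asks of it. All efficacy endpoints are plate counts from samples collected in the sampling solution, diluted in PBW and plated within 30 minutes of collection, so the claim that these fluids are harmless to the organisms should rest on a test able to show otherwise.

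**Working it through.** **Inputs.** The plan states no power or sample-size figure for this test. The only figure to interpret is the 0.20 log10 limit (item 8.4). The fluids and agars, from items 8.2.1 to 8.2.4, are:

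| Test | Suspending fluid | Agar |
|---|---|---|
| 1, effectiveness | sampling solution recovered from treated skin | TSA+N |
| 2, toxicity | sampling solution alone | TSA+N |
| 3, viability | PBW | TSA |
| 4, article control | test or control article | TSA |

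Section 3.4.3 gives TSA+N as 0.5% Tween 80 and 0.07% lecithin. Section 5.2.2 names lecithin, Tween 80 and Tamol in the sampling solution, with amounts redacted.

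**Step 1: what the limit allows.** 1 − 10^(−0.20) = 1 − 0.631 = 0.369. Against a neutralizer-free control, the rule tolerates a loss of 37% of organisms.

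**Step 2: what the rule measures.** Let m be the log10 count with no neutralizer loss, x the true log10 loss caused by the sampling solution, kx the loss caused by PBW, and a the further loss from TSA+N relative to TSA. Any loss during inoculum dilution in PBW is common to both tests and cancels.

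- Test 3 = m − kx
- Test 2 = m − x − a
- Test 3 − Test 2 = (1 − k)x + a

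The agar term a is fully visible. The fluid term is visible only in the proportion 1 − k.

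**Step 3: largest true loss that passes.** With a = 0, the rule passes when x ≤ 0.20/(1 − k). The value of k is an assumption, taken from 0 to 1 because the PBW composition is redacted.

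| k | 0.20/(1 − k), log10 | Loss, 1 − 10^(−x) |
|---|---|---|
| 0 | 0.20 | 37% |
| 0.25 | 0.27 | 46% |
| 0.5 | 0.40 | 60% |
| 0.75 | 0.80 | 84% |
| 1 | no limit | any |

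For example, a true loss of 0.30 log10 shows as 0.30 at k = 0 (fails), 0.15 at k = 0.5 (passes) and 0.00 at k = 1 (passes). A true loss of 0.50 shows as 0.25 at k = 0.5 and still fails.

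**Step 4: does a masked loss reach the endpoint?** If neutralizers remove b log10 at baseline and c log10 after treatment, the observed reduction equals the true reduction plus (c − b). With b = c the effect is zero.

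**The case against.** The strongest reply is that this may be a naming slip. The authors mark neutralizer-containing agar with +N, leave PBW unmarked, and give Test 3 plain TSA, so they may have meant, or used, plain Butterfield's water. That is possible, but no passage says so, and both the definition and the supply list point the other way.

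Several further points limit the consequence, and they stand in part.

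- **Agar contrast.** TSA+N contains two of the three additives named in the sampling solution. Growth inhibition by them in the agar would lower Test 2 relative to Test 3. What remains hidden is short-contact loss in the fluids.
- **Different fluids.** Nothing visible shows that Tamol is in PBW. Effects of ingredients found only in the sampling solution remain measurable.
- **Other signals.** Test 3 is counted within one minute and again at 30 minutes, so a progressive loss in PBW would appear in the data, although no acceptance rule covers that fall. Item 8.4(g) checks the inoculum level, but from the Test 3 count, itself taken in PBW, against a redacted target. The growth promotion control in Section 5.2.4 tests agar, not fluids.
- **Test 1.** That rule asks whether residual product is still active. A neutralizer loss common to Tests 1 and 3 cancels, and residual product activity can still show, so a reader should not infer that the effectiveness rule fails in the same way.

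A reader might also infer that responder rates of the active products are inflated. By Step 4 this needs organisms damaged by the product to be more sensitive to the neutralizers than baseline flora. No passage supports that, and Tests 2 and 3 could not reveal it even if repaired, because they use a laboratory culture never exposed to product.

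**Conclusion.** The point holds as a fault in the toxicity rule as written: the control is not neutralizer-free, so the rule cannot detect short-contact toxicity that PBW and the sampling solution share. The true loss that can pass ranges from the intended 0.20 log10 (37%) at k = 0 to 0.80 log10 (84%) at k = 0.75, and is unbounded only at k = 1. These figures assume no agar effect and a value of k that the documents do not allow anyone to fix.

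Two stronger conclusions are not supported. It is not shown that any degree of toxicity would pass, since that requires PBW and the sampling solution to have equal effect. Nor is it shown that log10 reductions or responder rates are biased, since an equal loss at baseline and after treatment cancels. The wording mismatch is certain; its practical effect is unknown. It should be corrected and resolved in the final report, where Section 5.2.5 already requires the validation data.

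**What to change.** **In Appendix 14.10:** specify neutralizer-free Butterfield's phosphate buffered water, under its own name, for the Test 3 suspension and for diluting the inoculum, and add it to item 6. Keep the 0.20 log10 limits. PBW with neutralizers can stay for serial dilution of study samples.

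**Because testing is complete** (Amendment 6 says so, and Deviation 1 reports how the validation was plated): state in the final report which fluid was used in Test 3 and for the inoculum. If it was plain buffer, correcting the wording is enough. If it contained neutralizers, rerun Tests 2 and 3 in vitro from one inoculum preparation, with plain buffer and PBW side by side as control suspensions, to show whether PBW and the sampling solution are each non-toxic against plain buffer.

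The Test 1 counts already obtained should not be compared directly with a new Test 3. They come from a different inoculum preparation, and that difference would be mixed into a 0.20 log10 limit. A new Test 1 would need fresh samples from treated skin.

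**Cost:** one additional buffer, a wording change and, if a rerun is needed, a few in-vitro plates with no subjects. The downside is that the sampling solution could fail a test it now passes.
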